13.1 Analysis populations

All primary and secondary analyses will be conducted in two (2) study cohorts:

1. Efgartigimod cohort: patients with an MG diagnosis and who have initiated efgartigimod for the treatment of MG
2. Reference cohort: patients with an MG diagnosis and who have not initiated efgartigimod, but who are on any other therapy for the treatment of MG

In the exploratory analysis, the long-term risk of malignancies will be evaluated in:

- FcRn cohort: patients with an MG diagnosis and who have initiated other FcRn antagonists for the treatment of MG

13.2 Primary analysis

The IRR and corresponding 95% CIs will be used to compare the malignancy events among the efgartigimod exposed cohort vs. the reference cohort. The calculations will be performed separately for each individual database and across all three (3) databases as a meta-analysis according to published methods.

A quasi-Poisson regression model will be used to estimate the incidence rate ratio between cohorts with number of event occurrences as the response variable, cohort and age as covariates and follow-up time as offset. Scale/overdispersion parameter will be used to account for potential over- or under-dispersion.

In addition, the balance of baseline measures, including matching variables (i.e. age, sex, CCI and duration of previous MG treatment) and other demographic and disease characteristics, will be assessed. The imbalanced measures which are considered to be potential confounders based on clinical judgement will be added to the quasi-Poisson model as additional covariates.

- Age will be adjusted as a covariate in the quasi-Poisson model to account for the increased malignancy risk over time, no matter balanced or not. And age-specific incidence rates and incidence rate ratio between cohorts can be calculated.
- Concomitant and/or previous use of monoclonal antibody will be adjusted as a covariate in the quasi-Poisson model to account for any potential imbalance.

The primary analyses will be performed on an “as-treated” basis. To this end, patients will contribute person time until the first occurrence of the following events: death, loss to follow-up, end of study period, or a switch from any MG treatment to efgartigimod (for the reference cohort). For the analyses performed based on “as-treated” basis, the time before switching to efgartigimod for the reference cohort will be counted toward the overall person-time but not the time after switching.

A sensitivity analysis based on the intention-to-treat principle will be conducted to ensure the continued monitoring of safety outcomes, irrespective of any treatment modifications throughout the follow-up period. For the sensitivity analyses performed based on “intent-to-treat” basis, both the time before and after switching will be counted. Sensitivity analysis will be described as noted in section 13.5.

Duration of follow-up time with and without censoring by cohort will be summarized and compared. The percentages of patients with different reasons of censoring will be summarized by cohort. Details of the analysis will be given in the Statistical Analysis Plan

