9.1 Study design

This multinational, longitudinal database cohort study will identify patients who are newly treated with efgartigimod and have a diagnostic code for MG (efgartigimod cohort). A patient will be considered an efgartigimod exposed patient if he/she has received at least one (1) dose of efgartigimod.

For each patient entering the efgartigimod cohort, the date of the first efgartigimod exposure in the database (either through an IV infusion or SC injection) will be their index date for the study. Only new users of efgartigimod will be included in this cohort, that is, a patient who receives a first prescription, or first dispensing, or has a first procedure code for efgartigimod during the study period and without a prescription or a dispensing or a procedure code for efgartigimod in the previous 12 months.

A reference cohort will also be selected with a 2:1 ratio to the efgartigimod cohort to provide an overall, real-world assessment of malignancy risk in patients receiving efgartigimod. The reference cohort will consist of patients with a diagnosis code for MG without efgartigimod exposure but is on any other therapy for the treatment of MG during the study period. The index date for each patient in the reference cohort will be assigned as the same index date as the corresponding matched efgartigimod patient.

Identification of patients in the reference cohort will be based on selected matching variables in the patient's history (prior to and including the index date) or within 6 months of the index date. More specifically, within each database, efgartigimod initiators will be matched 2:1 (reference: efgartigimod) by (1) age at index date (+/- 5 years), (2) sex, (3) Charlson Comorbidity Index (CCI)² and (4) duration of prior use of other MG treatment as matching variables prior to and including the index date or within 6 months of the index date.

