9.6 Covariates

This study is designed to describe real-world outcomes associated with the use of efgartigimod. The covariates to be collected include any clinical characteristics, medication use, and medical procedures coded in the databases that could be used to provide a complete description of the cohorts and subpopulations. Baseline covariates observed in the patient’s medical history and other relevant factors prior to the study drug initiation will be assessed.

It is anticipated that not all variables can be collected in the three (3) selected databases; therefore, all covariates will be collected based on data availability. The following list of *a priori* covariates will be evaluated. A more detailed description of relevant covariates and their use in the analysis will be described in the SAP.

1. Cohort identification

- Date(s) of a diagnosis of MG (health care setting) to approximate disease duration (new-/old-onset)

2. Demographic factors

- Gender
- Ethnicity/race (if allowed)
- Patient's age at his/her index date
- Thymoma (with or without thymectomy), if present in database (date, indication, histology)
- [Supplementary variables]
 - Comorbidities
 - CCI will be calculated based on comorbidities identified in the lookback period in the selected databases.
 - Serological testing of MG diagnosis, if available
 - MG Disease severity, if available

3. Lifestyle variables⁴, if available

- Smoking
- Body mass index (BMI)
- Alcohol consumption

4. MG treatment

- Prior and current treatments, e.g.
 - Anticholinesterase agent
 - Corticosteroids
 - Chronic non-steroidal immunosuppressants
 - Monoclonal antibodies
 - Plasmapheresis/plasma exchange
 - IVIg therapy
- Duration of exposure of prior and current treatments, if available
- [Supplementary variables]

⁴ May only be available in EMR database(s) but not claims administration databases.

- Cumulative dose for each line of therapy, if available, and if not, number of distinct concomitant MG treatments (mono-, double or triple therapy)

5. Concomitant treatments

- Type of treatment and duration (for selected concomitant medications)
- [Supplementary variables]
 - Duration of exposure for each treatment
 - Cumulative dose of each treatment, if available

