Since the variation under a random-effect model assuming heterogeneity across databases consists of both within-database and between-database variation and the number of patients will only impact the within-database variance, a two-step method for sample size calculation is conducted: 1) calculate the unadjusted sample size using inequality test assuming no heterogeneity among databases as if all patients were from one single database; 2) calculate the adjusted sample size by multiplying an adjustment factor to the unadjusted sample size assuming moderate heterogeneity. The feasibility of patient accrual based on projected cumulative number of patients in the databases is discussed considering factors that may impact the final number of patients, such as loss to follow-up, malignancy history, etc.

A real-world study using Optum database conducted by argenx showed malignancy incidence rate of 73.6 per 1,000 PY in MG population (data not published). An exploratory analysis using the result from the eculizumab Phase III study (NCT01997229) and its extension study (NCT02301624) ([Mantegazza 2021](#) and Results from clinicaltrials.gov) showed malignancy incidence rate of 42.0 per 1,000 PY for eculizumab-treated patients (data not published). With this wide range of observed incidences in MG populations, a spectrum of malignancy incidence rates was explored with upper and lower bound of 73.6 and 42.0 per 1,000 PY.

Under the fix-effect model assuming a common effect size and variance it is demonstrated that the variance of the combined effect will be the same regardless of the distribution of sample size in each database ([Borenstein 2010](#)). Therefore, the sample size calculation can be conducted based on the overall number of patients. Using a two-sided inequality test for two (2) Poisson rates ([Zhu 2017](#)) the unadjusted sample size is shown in Table 3 with 5% significance level, >85% power and rate ratio 1.3 under alternative hypothesis. The follow-up time is assumed to be 6 or

8 years based on the study design. The calculation is conducted using the power and sample size software PASS 2023. A total of 679 efgartigimod patients are needed assuming no heterogeneity (Power Analysis and Sample Size Software (2023) (NCSS, LLC. Kaysville, Utah, US [ncss.com/software/pass]).

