To account for the increased variance owing to between-database variation under random-effect model if heterogeneity exists, the unadjusted sample size is multiplied by the adjustment factor of $1/(1 - I^2)$ (Wetterslev 2009) where I^2 is the heterogeneity measure. Assuming moderate heterogeneity of $I^2 = 0.5$ the adjustment factor equals to 2. The adjusted sample size is therefore two (2) times of the unadjusted sample size and shown in Table 3. A total of 1358 efgartigimod-treated patients are needed with a rate ratio of 1.3 under alternative hypothesis, 6-year follow-up and background rate of 42.0 per 1,000 PY to achieve >85% power.

Table 3. Sample size calculation

Background Rate in 1000PY	Follow-up Year	Rate Ratio under Alternative Hypothesis	Unadjusted Sample Size in Efgartigimod Cohort	Adjusted Sample Size* in Efgartigimod Cohort
42.0	6	1.3	679	1358
	8	1.3	509	1018
60.0	6	1.3	475	950
	8	1.3	357	714
73.6	6	1.3	384	768
	8	1.3	288	576

* Adjusted sample size = unadjusted sample size × 2, where 2 is calculated from $1/(1 - I^2)$ assuming moderate heterogeneity of $I^2 = 0.5$

To further demonstrate the ability to detect difference between two (2) cohorts, power analysis is conducted using two-sided inequality test (H_0 : rate ratio=1 vs. H_a : rate ratio \neq 1) for two (2) Poisson rates (Zhu, 2017) with 5% significance level and rate ratios of 1.2, 1.3, 1.4, 1.5, 2, 3 and 4. Table 4 shows that there are >80% power in most scenarios under the adjusted sample size of 1358.

Table 4. Power calculation

Background Rate in 1000PY	Follow-up Year	Rate Ratio under Alternative Hypothesis	Power
42.0	6	1.2	54.20%
		1.3	86.13%
		1.4	97.90%
		1.5	99.84%
		2	100.00%
		3	100.00%
		4	100.00%

Background Rate in 1000PY	Follow-up Year	Rate Ratio under Alternative Hypothesis	Power
	8	1.2	66.46%
		1.3	94.03%
		1.4	99.60%
		1.5	99.99%
		2	100.00%
		3	100.00%
		4	100.00%
60.0	6	1.2	69.45%
		1.3	95.36%
		1.4	99.76%
		1.5	100.00%
		2	100.00%
		3	100.00%
		4	100.00%
	8	1.2	81.34%
		1.3	98.76%
		1.4	99.98%
		1.5	100.00%
		2	100.00%
		3	100.00%
		4	100.00%
73.6	6	1.2	78.39%
		1.3	98.17%
		1.4	99.96%
		1.5	100.00%
		2	100.00%
		3	100.00%
		4	100.00%
	8	1.2	88.69%
		1.3	99.67%
		1.4	100.00%
		1.5	100.00%
		2	100.00%
		3	100.00%
		4	100.00%

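### The primary model's age term, read as age at index, cannot adjust for malignancy risk that rises during follow-up; with switch censoring in the reference cohort only, the IRR can be biased, probably upward by a few percent

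*Protocol*

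**What the plan says.** Protocol section 13.2 specifies a quasi-Poisson regression with "number of event occurrences as the response variable, cohort and age as covariates and follow-up time as offset". It keeps age in the model whether or not age is balanced, and gives the reason: "Age will be adjusted as a covariate in the quasi-Poisson model to account for the increased malignancy risk over time". It adds that age-specific rates and rate ratios can be calculated.

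Section 13.2 does not say which age it means. It lists age among the baseline matching variables. Section 9.1 matches on age at the index date within 5 years, and section 9.6 lists the covariate as the patient's "age at his/her index date". Age at index is therefore the natural reading.

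The primary analysis is as-treated. Person-time ends at death, loss to follow-up, end of study, or "a switch from any MG treatment to efgartigimod (for the reference cohort". No corresponding treatment-change rule is stated for efgartigimod patients. Section 9.2.2 adds that switchers leave the reference group and are counted in the efgartigimod group, and that cohorts and matching are redefined at each interim analysis. Section 9.2.2.1 expects switching to occur.

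**The concern.** A count with a log follow-up offset and a fixed covariate treats each patient's rate as constant over the whole window. Index age separates patients who start older from those who start younger. It says nothing about the same patient being ten years older at the end of follow-up, so the term cannot serve the purpose section 13.2 gives it. Age-specific rates built on it would also credit an event ten years after index to the patient's age at entry.

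This would matter little if both cohorts were observed over the same time since index. The one-sided censoring rule can break that symmetry. If other losses are equal and switchers are not replaced, reference person-time is shorter and younger. The model then compares average rates over windows of different length instead of rates at the same age. In a safety study sized for a rate ratio of 1.3, that could be read as a small drug effect.

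**Working it through.** **Design figure.** Section 11 uses "Using a two-sided inequality test for two (2) Poisson rates" with "5% significance level, >85% power and rate ratio 1.3 under alternative hypothesis", a "background rate of 42.0 per 1,000 PY", 6 years of follow-up in both cohorts, and 2:1 matching (section 9.1: "efgartigimod initiators will be matched 2:1 (reference: efgartigimod"). For 679 efgartigimod patients (the unadjusted size; 1,358 after the heterogeneity factor of 2):

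- expected events: 679 × 6 × 0.042 × 1.3 = 222.4 and 2 × 679 × 6 × 0.042 = 342.2
- variance of log IRR: 1/222.4 + 1/342.2 = 0.00742, so SE = 0.0861
- power: Φ(ln 1.3 / 0.0861 − 1.96) = Φ(1.086) = 86.13%, as in Table 4.

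This calculation gives both cohorts equal follow-up and constant rates.

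**IRR under no drug effect.** Take equal index age, a rate proportional to exp(b·t) at time t since index, loss h per year in both cohorts, and extra switch censoring s per year in the reference cohort. The model compares average rates:

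IRR₀ = [B(h)/A(h)] / [B(h+s)/A(h+s)], where A(k) = (1 − e^(−kT))/k is mean follow-up and B(k) = (e^((b−k)T) − 1)/(b − k), which equals T when b = k.

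The protocol gives none of b, s or h. All three are assumptions. With b = 0.05, s = 0.10, h = 0.05:

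| T (years) | Mean follow-up, efgartigimod / reference | Average rate relative to index, efgartigimod / reference | Null IRR | Efgartigimod person-time older by |
|---|---|---|---|---|
| 6 | 5.18 / 3.96 | 1.1575 / 1.1405 | 1.015 | 0.29 y |
| 8 | 6.59 / 4.66 | 1.2133 / 1.1820 | 1.026 | 0.52 y |
| 10 | 7.87 / 5.18 | 1.2707 / 1.2205 | 1.041 | 0.79 y |

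**Range at 10 years, h = 0.05.**

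- b = 0.03, s = 0.05: 1.012
- b = 0.05, s = 0.15: 1.061
- b = 0.08, s = 0.10: 1.067
- b = 0.08, s = 0.15: 1.4819/1.3470 = 1.10
- b = 0.08, s = 0.20: 1.132

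On the log scale, the 5%/10% case is ln 1.041/ln 1.3 = 0.15 of the design effect. The 8%/15% case is ln 1.10/ln 1.3 = 0.36.

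**Rejection under the null, 5%/10% case.** With 1,358 versus 2,716 patients in one pooled dataset without heterogeneity, it is about 5.5%, 7% and 10% at 6, 8 and 10 years. At 10 years, expected events are 1,358 × 7.87 × 0.042 × 1.041 ≈ 467 and 2,716 × 5.18 × 0.042 ≈ 591. SE is then 0.062, and ln 1.041/0.062 ≈ 0.65.

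**What changes the sign or size.**

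- Switchers join the efgartigimod cohort with a new index date and no new matched references: null IRR 0.997 to 1.003 at 2–5% switching and 1.009 to 1.025 at 10%, over 10 years with slopes of 3–8%.
- Extra loss or death among efgartigimod patients equal to the switch rate: no bias. With 15% versus 5% loss, 5% switching and a 5% slope, the null IRR at 10 years is 0.98.

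**Check of the remedy.** In simulations of the quasi-Poisson model, the null IRR was 0.99 to 1.02 with age taken at mid-follow-up and 0.99 to 1.01 with person-time split by attained age. With index age and no switching it was 0.99 to 1.00.

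**The case against.** A reader might infer that the primary IRR must exceed 1 when the drug has no effect, by as much as a third of the design effect, with false-positive rates of 12% to 32%. The documents do not support that. The slope, switch rate and losses are all assumed, and the upper figures need the steepest slopes and heaviest switching. Calculations with fixed cohorts also omit the re-entry rule in section 9.2.2. At 10% switching, about 2,716 × 5.2 × 0.10 = 1,412 reference patients would switch, more than the 1,358 in the efgartigimod cohort, and would bring later start dates and shorter windows. Rejection rates from one pooled dataset do not describe a meta-analysis of three databases planned for I² = 0.5, in a study that section 11 calls exploratory. These points stand, and they limit the claim to a possible bias of uncertain size.

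Other planned analyses help only partly. The intention-to-treat analysis removes the asymmetry, but by counting efgartigimod-exposed time as reference time. Section 13.4 also presents the sensitivity analyses without inferential intent. The Cox model in section 13.5 compares patients at the same time since index and would absorb much of the drift, but it is a sensitivity analysis to an exploratory one. The follow-up comparison in section 13.2 is descriptive. None of them corrects the primary IRR.

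It can also be said that section 13.2 never writes the words at index, and that the SAP could time-update age. That is possible. However, section 13.2 already fixes the count, the offset, the covariate and its purpose, and the only age defined elsewhere for matching or adjustment is the index age.

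**Conclusion.** The point holds in a limited form. On the natural reading, the age term does not do what section 13.2 says it is for. That conclusion rests on the protocol's wording and needs no assumed figure. The consequence for the primary IRR is conditional: with one-sided switch censoring it can be biased, probably upward and by a few percent. The central illustration is 1.015 to 1.041 over 6 to 10 years. It assumes equal 5% loss, a 5% age slope, 10% switching and no re-entry of switchers. Re-entry can bring it close to 1, and differential loss or death can take it below 1. Follow-up longer than 10 years would enlarge it. Sections 9.1 and 9.2.2 allow accrual of up to 5 years and follow-up until 10 years after the last patient is selected, although a footnote in section 6 describes a 10-year study period.

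**What to change.** In section 13.2, split each patient's person-time into attained-age bands, for example of 1 or 5 years. Fit the same quasi-Poisson model to the split records, with time-updated attained age in place of, or in addition to, age at index, and with log person-time per band as the offset. Report the age-specific incidence rates and rate ratios by attained age.

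The cost is a change of wording and routine additional programming on data already held. No patients or events are lost.

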13.3 Subgroup analysis

Analyses of the primary outcome will be repeated for each of the following subpopulations:

1. Elderly - aged 65 and older years at their index date
2. Chronic use (i.e., ≥ 1 year) of corticosteroids

13.4 Sensitivity analysis

Sensitivity analyses may be considered for scenarios that patients remain on efgartigimod who do not switch vs. patients who take efgartigimod and switch to a different therapy. The sensitivity analysis in this study will be exploratory in nature. Results from subgroup and sensitivity analyses will be presented and discussed in the final report, but it is not the intent to provide any inferential statistics.

- Intention-to-treat analysis will be carried out, in which patients will be censored at death, loss to follow-up, end of study period.
- Sensitivity analyses will be performed for subgroups with 1-2, 2-3 and >3 years lookback period in the US database if sample size allows.
- A sensitivity analysis will be performed for users of efgartigimod as a first-line treatment only if the number of patients allows for it.
- Depending on the number of efgartigimod-using MG patients identified as likely to have been included in the clinical trials, a sensitivity analysis will be carried out by including only patients with a minimum wash-out period of 2 months after the end of the clinical trials.
- To evaluate the potential bias of including events of malignancy occurring within the first year of initiation of efgartigimod or a reference drug, a sensitivity analysis will be conducted that excludes events occurring within the first 12 months after a patient’s study index date.
- To take into account the various reference treatments to which efgartigimod can be added and compared a sensitivity analysis will be performed. In this analysis the reference cohort will be defined according to the type of concomitant treatment given

in addition to efgartigimod (if the number of patients allows). The risk of cancer will thus be assessed between the following treatment groups:

- Users of efgartigimod added to symptomatic treatment (i.e. anticholinesterase agent) vs. Users of symptomatic treatment;
- Users of efgartigimod added to corticosteroids vs. Corticosteroids users;
- Users of efgartigimod added to chronic non-steroidal immunosuppressants vs. Chronic non-steroidal immunosuppressants users;
- Users of efgartigimod added to any chronic immunosuppressants (including corticosteroids) vs. any chronic immunosuppressants users;
- Users of efgartigimod vs other monoclonal antibodies users
- Users of efgartigimod without concomitant or previous use of another monoclonal antibody vs users of other MG therapies without concomitant or previous use of any monoclonal antibody.

In this analysis patients will contribute person time until the first occurrence of the following events: death, loss to follow-up, end of study period, or a switch from any MG treatment to efgartigimod (for the reference cohort). For the sensitivity analyses performed based on “intent-to-treat” basis, both the time before and after switching will be counted.

Additional considerations regarding the sensitivity analyses will be addressed in the SAP.

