Patient accrual into the study will begin following the launch of efgartigimod (differs by country), allowing for a lag between actual exposure dates and appearance of the medication record/procedure in each of the data sources, and will continue for up to 5 years via database refreshes (assumed to be annual). To achieve a desired sample size across all databases, a minimum of approximately 1,358 patients will be included in the efgartigimod cohort and 2,716 matched patients in the reference cohort. Accrual of patients into the study cohorts will be monitored annually. Patients will be followed from study entry to at least 10 years following inclusion in the study. If efgartigimod uptake is slower than expected, patient accrual may need to be extended to reach the required sample size.

² CCI is a method of predicting mortality by classifying or weighting comorbid conditions and has been widely utilized by health researchers to measure burden of disease and case mix. Nineteen (19) conditions are included in the index. Each condition is assigned a weight from 1 to 6, based on severity of the disease and estimated 1-year mortality, and these weights from the comorbidities were added to give a singular numeric score which will act as a way of quantifying current health status.

The study will assess the occurrence of any malignancy according to International Classification of Diseases, Tenth Revision (ICD-10) diagnosis codes, which will be grouped according to the ICD-10 classification system (or to the ICD revision valid at time of analysis). More specifically, the first incidence of and time to any malignancy (incidence rate of events of malignancy per PYs exposed in the efgartigimod treated cohort compared to the reference cohort), as well as incidence rate ratio (IRR) will be estimated.

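### The optional Section 13.4 contrast of efgartigimod stayers with switchers groups patients by a post-index event and, run as worded, can give a rate ratio far from 1 with no drug effect (minor)

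*Protocol*

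**What the plan says.** Section 13.4 of the protocol opens with an optional contrast inside the efgartigimod cohort. It permits, without requiring, an analysis of "scenarios that patients remain on efgartigimod who do not switch vs. patients who take efgartigimod and switch to a different therapy". The section calls these analyses exploratory and says "it is not the intent to provide any inferential statistics", but it also says their results will appear and be discussed in the final report. It closes with "Additional considerations regarding the sensitivity analyses will be addressed in the SAP".

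The only person-time rule for switching concerns the other direction. In the as-treated primary analysis (Section 13.2), "patients will contribute person time until the first occurrence of the following events: death, loss to follow-up, end of study period". One further item ends the list and applies to reference patients alone: starting efgartigimod after another therapy. For those patients the time before the switch counts and the time after it does not. Section 13.4 repeats this list after its comparisons by concomitant treatment. Section 9.2.2 likewise deals only with reference patients who start efgartigimod, and Section 9.2.2.1 refers the handling of switches to Section 13 and the SAP.

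On events, Section 9.1 speaks of "the first incidence of and time to any malignancy". The Section 13.2 list does not name malignancy as an end of person-time.

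**The concern.** Switching away from efgartigimod happens after the index date. If patients are labelled stayer or switcher over the whole of follow-up and person-time runs from index, two distortions are possible, depending on how events are counted.

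- If counting stops at first malignancy and only earlier switches are seen, a switcher must have been malignancy-free up to the switch. All that event-free time is credited to the switchers, and stayers look worse.
- If follow-up continues past the malignancy and a cancer makes a change of therapy more likely, patients with cancer move into the switcher group, and switchers look worse.

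This is the one analysis in the protocol that sets staying on efgartigimod against leaving it. The primary rule does not end an efgartigimod patient's person-time at a switch away, so a reader of the final report may look here for a check on that. A spurious ratio in either direction could be taken for a safety signal or for reassurance, even without a p-value.

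**Working it through.** **Inputs.** From Section 11: malignancy "upper and lower bound of 73.6 and 42.0 per 1,000 PY", follow-up of 6 or 8 years, rate ratio 1.3. From Section 9.2.2: follow-up to 10 years after the last patient selected. Assumed, because the protocol gives no figure: switching at 5 to 20% a year, death at 30 per 1,000 person-years, and the effect of malignancy on switching. The true stayer/switcher ratio is set to 1.

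**The plan's own figure.** No figure is stated for this contrast. The sample size reproduces, so the Section 11 inputs are read as intended. With n = 679, T = 6, rates 0.042 and 0.0546 and two reference patients per efgartigimod patient:

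- V = (1/6)(1/0.0546 + 1/0.084)/679 = 0.00742, square root 0.0861
- power = Φ(ln 1.3/0.0861 − 1.96) = Φ(1.086) = 86.13%, as in Table 4 (which, with the variance doubled, uses 1,358)

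**Case 1: counting stops at first malignancy, switches seen only before it.** Take malignancy λ = 0.042, switching s = 0.12, death μ = 0.03 and T = 8 years, with independent exponential times. Let a = λ + s + μ = 0.192 and b = λ + μ = 0.072, so exp(−aT) = 0.2152 and exp(−bT) = 0.5621. Per patient:

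- Stayer events = (λ/a)(1 − exp(−aT)) = 0.21875 × 0.7848 = 0.1717
- Stayer person-years = b[1 − exp(−aT)(1 + aT)]/a² + T exp(−aT) = 0.887 + 1.722 = 2.609
- All events = (λ/b)(1 − exp(−bT)) = 0.2554; all person-years = (1 − exp(−bT))/b = 6.081
- Switcher events = 0.2554 − 0.1717 = 0.0837; switcher person-years = 6.081 − 2.609 = 3.472
- Rates per 1,000 person-years: stayers 65.8, switchers 24.1, ratio 2.7

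Simulation at the same inputs gives 65.8 and 24.2, ratio 2.72. With switching at 5 to 20% a year over 6 to 10 years, the ratio is 2.2 to 3.8. Without deaths, and at both 42.0 and 73.6 per 1,000 person-years, it is 2.19 to 4.18.

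**Same data, time split at the switch.** Pre-switch person-years = (1 − exp(−aT))/a = 0.7848/0.192 = 4.087, with the same 0.1717 events: 42.0 per 1,000. Post-switch person-years = 6.081 − 4.087 = 1.994, with 0.0837 events: 42.0 per 1,000. The ratio is 1.0. The whole artefact is the 4.087 − 2.609 = 1.478 person-years per patient that switchers spent before switching.

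**Case 2: follow-up continues to death or 8 years, and any switch in that time defines a switcher.** Simulation with λ, s and μ as in Case 1:

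| Switching rate after malignancy | Stayer/switcher ratio |
|---|---|
| unchanged | 1.01 |
| doubled | 0.62 to 0.63 |
| tripled | 0.43 (19.2 vs 44.4 per 1,000) |

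**Both effects together.** If counting stops at first malignancy but a share of malignancies also prompt a switch, the effects oppose each other. Over 42.0 and 73.6 per 1,000, 6 to 10 years and 5 to 20% switching, without deaths, the ratio is 0.71 to 2.90 at a 25% share, 0.33 to 1.89 at 50% and 0.13 to 1.03 at 75%.

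**Time-varying status.** With switching unrelated to malignancy, the null ratio is 0.998 to 1.006 in every simulated scenario. With switching tripled after malignancy it is 1.01, because a cancer diagnosed before the switch it prompts is already pre-switch.

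**Lag after the switch.** Moving only the events of the lag window to the pre-switch category gives a null ratio of about 1.20 (6 months) or 1.44 to 1.45 (12 months). Moving the events and the person-time together restores 1.00.

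**The case against.** The best defence is that the protocol does not yet define this analysis. It "may be considered" is the tone of the sentence: no estimator or person-time rule is given, and Sections 9.2.2.1 and 13.4 leave details to the SAP, which could adopt a landmark or time-varying status without contradicting the protocol. The list in Section 13.2 governs efgartigimod against reference, so person-time from index for stayers and switchers is an inference. The sentence could also mean two scenarios, each set against the reference cohort. Nothing primary depends on it.

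Most of this stands and sets the weight of the point. It does not remove it. The objection is to the grouping that the protocol itself names, not to detail left for later: a SAP that follows the sentence literally reproduces the bias, and under the two-scenario reading patients would still be selected by a future switch.

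Stronger readings that a reader might infer are not supported:

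- That the comparison is always biased. If any later switch counts and switching is unrelated to malignancy, the ratio is about 1.0.
- That early deaths among stayers drive the result. With deaths included, Case 2 with unchanged switching gives 1.01, and dropping deaths from Case 1 moves the ratio only from about 2.7 to 2.8.
- That nothing else in the protocol bears on time after leaving efgartigimod. Follow-up there continues in the primary and intention-to-treat analyses, exposure duration is a secondary objective, and Section 9.4 defines discontinuation and intermittent use.

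**Conclusion.** The concern holds as a minor point. Section 13.4 names a contrast between groups defined after index, and no rule covers switches away from efgartigimod. With no drug effect, the literal comparison can return about 2.2 to 3.8 if counting stops at first malignancy, or about 0.4 to 0.6 if follow-up continues and malignancy doubles or triples switching. Both are further from 1 than the rate ratio of 1.3 used for the sample size.

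The malignancy rate and follow-up are the protocol's. The switching and death rates and the link from malignancy to switching are assumptions, so size and direction in the real data are unknown. The documents do not support reading this as a flaw in the primary analysis, the sample size or any inferential result: the analysis is optional, exploratory and non-inferential.

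**What to change.** In Section 13.4, replace the stayer and switcher groups by time-varying switch status. Each efgartigimod patient contributes person-time and events to a pre-switch category up to the switch date, and to a post-switch category from then on. This is the same split by date that Section 13.2 already uses to end reference time when a patient starts efgartigimod.

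If cancers already developing at the switch should not be charged to the later therapy, add a lag after the switch (for example 6 to 12 months) and assign both the events and the person-time in that window to the pre-switch category. Moving the events alone would create a new bias.

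Cost: one or two sentences in the protocol or SAP and slightly more programming. No change to cohorts, sample size or the primary analysis.
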